5.3.5.4 Persistent or Recurrent Adverse Events

A persistent AE is one that extends continuously, without resolution, between subject evaluation timepoints. Such events should only be recorded once on the Adverse Event eCRF (and Form, if appropriate). The initial severity (intensity or grade) of the event will be recorded at the time the event is first reported. If a persistent AE becomes more severe, the most extreme severity should also be recorded on the Adverse Event eCRF (and Form, if appropriate). If the event becomes serious, it should be reported to the Sponsor immediately (i.e., no more than 24 hours after learning that the event became serious; see Section 5.4.2 for reporting instructions). The Adverse Event eCRF if already completed should be updated by changing the event from "non-serious" to "serious," providing the date that the event became serious, and completing all data fields related to SAEs.

A recurrent AE is one that resolves between subject evaluation timepoints and subsequently recurs. Each recurrence of an AE should be recorded as a separate event on the Adverse Event eCRF (and Form if appropriate).

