### 17.1.1 Adverse Events

All AEs will be coded to the current version of Medical Dictionary for Regulatory Activities (MedDRA, the latest version) by F. Hoffmann-La Roche, Ltd.

All AE summaries will include only treatment emergent adverse events (TEAEs). Treatment-emergent adverse events are those which occur after the first dose of study drug. AEs starting prior to medication dosing in the first period will be regarded as pre-dose AEs (i.e. non-TEAEs).

TEAEs occurring following dosing in a specific analysis period but before dosing in the next analysis period will be attributed to that specific analysis period, thus to the last received treatment. If the time is missing for an AE on a dosing day then the AE will be attributed to the treatment given on that day.

All AEs (including non-TEAEs) recorded on the eCRF will be listed (including analysis period and treatment information). Pre-dose AEs will be presented in a separate listing. In addition, a separate listing of AEs leading to withdrawal from study will be provided.

TEAEs will be tabulated by system organ class and preferred term: one table with all TEAEs (number and percentage of subjects) overall and by treatment; one table with related TEAEs (number and percentage of subjects) overall and by treatment; one table with all TEAEs (number and percentage of subjects) by treatment and relationship to study drug; one table with TEAEs (number and percentage of subjects) by treatment and severity.

Subjects are counted once, per preferred term per treatment, for the most severe of multiple occurrences (in case of severity) or most drug-related event (in case of relationship) of a specific MedDRA term. AEs whose causal relationship was characterized as 'Yes'/'No' will be regarded as being related/not related to the study medication.

The following missing data will be imputed as defined (for calculations only / will not be presented):

- Missing AE start and / or end times for the calculation of onset and duration will be assumed to be at 00:01 for a start time and 23:59 for end times

- Missing AE severity or relationship will be assumed to be severe or related, respectively
- Missing AE start times for the determination of treatment emergence will be assumed to occur after treatment unless partial date documents the AE as happening prior to treatment

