- Missing AE start times for the determination of treatment assignment will be assumed to occur after treatment on the recorded date one minute after dosing
- Missing AE start date will be attributed to the treatment from analysis period 1 unless the AE end date occurs before first IMP administration

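### AEs with no start date default to the single dose, and an AE that begins in Period 1 and worsens under QD dosing is not counted under QD

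*SAP*

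**What the plan says.** SAP 17.1.1 places treatment-emergent AEs by onset. An event after dosing in one period and before dosing in the next "will be attributed to that specific analysis period, thus to the last received treatment". From the design and the labels in SAP 9.2.2, Period 1 is the single dose (A for 10 mg, C for 50 mg) and Period 2 is QD dosing (B and D).

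For an event without a start date, the rule is: "Missing AE start date will be attributed to the treatment from analysis period 1 unless the AE end date occurs before first IMP administration". Partial dates are mentioned only for deciding whether an AE is treatment-emergent, not for choosing the treatment. A missing clock time on a dosing day is handled separately: the event goes to that day's treatment.

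On persistent AEs, Protocol 5.3.5.4 says: "Such events should only be recorded once on the Adverse Event eCRF". On severity it says: "The initial severity (intensity or grade) of the event will be recorded at the time the event is first reported", and then: "If a persistent AE becomes more severe, the most extreme severity should also be recorded on the Adverse Event eCRF". A date of change is required only when the event becomes serious. For an AE that resolves and returns: "Each recurrence of an AE should be recorded as a separate event on the Adverse Event eCRF".

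In the severity table, SAP 17.1.1 counts a subject once per preferred term per treatment, at the most severe of several occurrences. The safety objective in SAP 5.2 names the 10 mg QD and 50 mg QD regimens.

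**The concern.** The missing-date rule ignores information the study will hold. AEs are sought at every contact (Protocol 5.3.1), with questions about change since the last visit (Protocol 5.3.2). An undated AE first mentioned at follow-up, after 14 daily doses and several contacts without it, still counts against one dose taken weeks before. Elsewhere in the same list the SAP takes the cautious side: missing severity becomes severe and missing relationship becomes related. Here the default favours the regimens that the safety objective is about.

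The second gap comes from two rules acting together. One record per persistent AE, placed by onset, means that an AE which starts after the single dose, is still present at the first Period 2 dose and then worsens produces nothing under B or D. Yet the Protocol's AE definition (5.2.1) includes worsening of an existing condition, and 5.3.5.9 makes the worsening of a condition present at screening an AE. The same worsening of a condition that began after the Period 1 dose yields no QD event in the tables.

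At stake is whether the by-treatment AE tables understate QD events.

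**Working it through.** The documents give no AE figure to reproduce, so the check has three parts: cases put through the rules, the likely error rate of the default, and the effect on a column.

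**1. Cases, 10 mg cohort (A = single dose, B = QD)**

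| Event | Where the rules put it | Comment |
|---|---|---|
| Known onset, Period 2 Day 5 | B | Correct |
| Onset in Period 1, resolves, recurs in Period 2 | A and B | Correct |
| Start date missing, ends Period 2 Day 10 | A | May have arisen under A or B; contact history not used |
| Mild onset Period 1 Day 3, persists, severe Period 2 Day 8 | A only | Worsening has no entry under B |
| Onset Period 2 Day 1, time missing | B | May move a pre-dose event towards QD |

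The third and fourth rows are the problem. The 50 mg cohort behaves the same way with C and D.

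**2. How often the missing-date default would be wrong**

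Inputs:
- Period 1 window, first dose to first Period 2 dose: T1 = 14 days (Protocol 3.1).
- Period 2 window: Day 1 to Day 14 is 13 days, plus 14 days (earliest follow-up, Protocol 3.1) to 21 days (end of AE reporting, Protocol 5.3.1). T2 = 13 + 14 = 27 to 13 + 21 = 34 days.
- r = daily rate at which undated AEs begin in Period 2 divided by that in Period 1. The documents do not give it; values below are assumptions.

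Share truly beginning in Period 2 = r × T2 / (r × T2 + T1):

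| r | T2 = 27 | T2 = 34 |
|---|---|---|
| 0.5 | 13.5/27.5 = 49% | 17/31 = 55% |
| 1 | 27/41 = 66% | 34/48 = 71% |
| 2 | 54/68 = 79% | 68/82 = 83% |
| 4 | 108/122 = 89% | 136/150 = 91% |

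The SAP sends all of them to Period 1, apart from those that ended before first dosing.

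**3. Effect on a column**

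Percentages use the subjects exposed within a treatment (SAP 9.1.3). With 8 per cohort, one subject is 1/8 = 12.5 points, taken from one column and added to another. This is a maximum: a column does not change if the subject already has that preferred term there.

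**4. Could the worsening still reflect the single dose?**

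The two Day 1 doses are 14 × 24 = 336 hours apart. At the half-life of about 46 hours in Protocol 1.2.1.1, that is 336/46 = 7.3 half-lives, leaving 0.5^7.3 = 0.6%. Worsening during Period 2 is therefore unlikely to be an effect of the Period 1 dose.

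**The case against.** A reader might infer that all the attribution rules push events towards the single dose. They do not. An AE with a known Period 2 start goes to QD, a recurrence is a new record, and the missing-time rule on Period 2 Day 1 acts the other way. Only the missing-date rule can move an AE that arises under QD.

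A reader might also infer that a worsened AE is tabulated under the single dose at its worst severity. That is the likely reading but is not stated. The Protocol records both initial and most extreme severity, and the SAP counting rule concerns several occurrences, not one persistent record. The QD column lacks the event under either reading.

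A third temptation is to count only days out of the unit, 4 after the single dose against 9 to 16 after QD dosing, which gives 9/13 = 69% to 16/20 = 80%. Nothing in the documents says that undated AEs arise only then.

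The stronger objections concern weight. Dosing is in-house, data are queried and verified, and an AE with no usable start date may never occur. Every AE is listed with its period and treatment, SAEs and withdrawals are listed separately, and the overall column is unaffected. With 16 subjects and no hypothesis tests, a careful reader of the listings could find a cross-period worsening. Placing one continuous AE by onset is also an explicit convention.

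These points limit the effect without removing it. The listing carries the same derived treatment label, and the overall column cannot show which regimen was involved.

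**Conclusion.** The concern holds for two specific cases. First, an AE with no start date is placed under A or C unless it ended before first dosing, even where the contact history points to QD dosing. At an equal daily rate that default would be wrong for 66% to 71% of such AEs, and for 49% to 91% over rate ratios of 0.5 to 4, which are assumed. Second, an AE that begins after the single dose and worsens under QD has no entry under B or D.

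Both cases understate the QD regimens. The number of affected AEs is unknown and may be zero. The change is worth making before database lock because it is cheap and the columns are small, not because a large bias has been shown.

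**What to change.** In SAP 17.1.1:

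- **(a) Missing start date.** Assign the treatment from any partial date, the end date, the contact at which the AE was first reported and the last contact without it. Where both periods remain possible, count the AE under the QD treatment, or flag it and show it under both.
- **(b) Worsening across periods.** For an AE ongoing at the first Period 2 dose that then worsens in severity or becomes serious, tabulate it at initial severity under A or C and at worst severity under B or D. This also settles which severity goes where.

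The cost is a few SAP sentences and a change to the ADAE derivation. Both severities are already collected, and the date is already required when an AE becomes serious. For other worsening, a date query may be needed for the few persistent AEs concerned; the eCRF is not among the documents, so it may already hold that date. Rule (a) may occasionally move to QD a Period 1 event that was first mentioned late.

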### 17.1.2 Deaths and Serious Adverse Events

A listing of deaths and other serious adverse events (SAE) will be provided by subject.

### 17.1.3 Laboratory Data

Clinical laboratory data will be presented using units from the study data tabulation model (SDTM) Controlled Terminology.

All laboratory data will be listed, including laboratory variables not listed in the protocol. A separate listing, including out-of-range values will also be provided. Normal ranges will be used directly from the clinical laboratory.

Descriptive statistics summarizing continuous laboratory results of clinical chemistry, hematology and urinalysis (observed and derived changes from baseline) by treatment and scheduled time will be provided.

Additionally, for CPK (chemistry) a frequency table for the following ranges will be added:

- $\leq 2$  times upper limit of normal (ULN)
- $> 2$  and  $\leq 5$  times ULN
- $> 5$  and  $\leq 10$  times ULN
- $\geq 10$  times ULN

For categorical urinalysis parameters frequency tables, showing the number of subjects in a category (n) and the percentage of the total number of subjects per treatment (N), will be provided. Sporadic urinalysis tests that were performed when abnormalities were observed (i.e. microscopy/sediment) will only be listed.

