4. MATERIALS AND METHODS

4.1 SUBJECTS

The target population will be healthy male (at least 4 male subjects enrolled per cohort) and female subjects, aged 18 to 65 years, inclusive, at screening. At least 4 subjects enrolled per cohort should be aged 18 to 50 years, inclusive, at screening.

A total of 8 subjects per cohort will be enrolled with the target of at least 6 subjects available for the primary PK analysis (i.e., having taken a single dose of balovaptan on Day 1 and completed all PK assessments up to Day 10). If the number of subjects providing PK data from the single or multiple dose parts of the study is lower than 6 for either cohort, more subjects may be enrolled. Enrolled subjects who withdraw from the study may be replaced at the discretion of the Investigator and Sponsor to ensure adequate numbers of evaluable subjects.

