#### 9.1.2 Imputation

Except for the substitution of any PK concentrations below the lower limit of quantification (LLOQ) (see [Section 16.2](#)) and missing start or end date/times of AEs for the calculation of onset and duration (see [Section 17.1.1](#)), any missing data will not be imputed.

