### 9.1.3 Descriptive Statistics

Unless otherwise indicated, continuous variables will be summarized with the following descriptive statistics:

- n (number of observations),
- nmiss (number of missing observations),
- (arithmetic) mean,
- SD,
- minimum (min) value,
- median, and
- maximum (max) value.

Categorical data will be summarized with frequencies and percentages. Percentages by categories will be based on the number of subjects exposed within a treatment.

For categorical data the categories will be presented in the tables exactly as they appear in the CRF / Database.

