### 9.1.4 Pooling

Summary statistics will be calculated by treatment (and time point, if applicable).

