### 17.1.5 Electrocardiograms

All ECG parameters (including changes from baseline) and the corresponding abnormalities and physician's conclusions will be listed by subject.

The observed measurements for all ECG parameters (including T-wave, U-wave) and the corresponding abnormalities will be listed for all time points. The means of triplicate measurements for continuous parameters and the change from baseline of the mean triplicate measurements at each scheduled time point will be listed by subject.

Descriptive statistics will be provided to summarize mean continuous ECG parameters (observed and changes from baseline) by treatment and scheduled time. A frequency table will be provided as well to summarize the ECG parameters by physicians conclusion (normal, abnormal not clinically significant, abnormal clinically significant). Additionally a frequency table for the following pre-specified QTcF ranges (for the rounded values) will be added:

ECG Parameter	Raw Value	(Positive) Change from Baseline
QTcF (msec)	$\leq 450$ , $> 450$ and $\leq 480$ , $> 480$ and $\leq 500$ , $> 500$	$\leq 20$ $> 20$ and $\leq 30$ , $> 30$ and $\leq 60$ , $> 60$

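### Frequency tables of measured safety results divide by everyone exposed, so any missing result lowers every category percentage, normal and abnormal alike

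*SAP*

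**What the plan says.** The general rule is in SAP 9.1.3: "Percentages by categories will be based on the number of subjects exposed within a treatment". SAP 17.1.3 restates it for categorical urinalysis parameters, where the table gives the count in each category and "the percentage of the total number of subjects per treatment (N").

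Three other frequency tables of measured results are planned, and none has a denominator of its own:

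- CPK bands, SAP 17.1.3: "Additionally, for CPK (chemistry) a frequency table for the following ranges will be added".
- ECG conclusion, SAP 17.1.5: a table to "summarize the ECG parameters by physicians conclusion (normal, abnormal not clinically significant, abnormal clinically significant").
- QTcF bands (value and change from baseline), SAP 17.1.5: "Additionally a frequency table for the following pre-specified QTcF ranges (for the rounded values) will be added".

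Apart from stated exceptions for PK values below quantification and for AE dates and times, SAP 9.1.2 says "any missing data will not be imputed". SAP 9.1.3 lists a count of missing observations among the statistics for continuous variables only. For categorical data it asks for frequencies and percentages, with the categories as they stand in the CRF or database, and it specifies no row for missing results. On layout, SAP 9.1.4 says "Summary statistics will be calculated by treatment (and time point, if applicable"). SAP 9.2.2 treats the single-dose and once-daily periods of each cohort as separate treatments, A to D.

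**The concern.** Exposed N is the natural denominator for adverse events and concomitant medications, because every exposed subject is under observation and having no record means having no event. A laboratory or ECG category is different: a subject can be placed in one only if a sample or tracing was taken. Dividing by exposed N mixes two things in one percentage, how results are distributed and how complete they are.

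The rule also sits awkwardly with the rest of the SAP. The continuous CPK and QTcF summaries (Tables 14.3.3.3 and 14.3.4.2) report the number of observations and the number missing, so they rest on subjects measured. The companion band tables (14.3.3.5 and 14.3.4.4) would rest on subjects exposed, with nothing in the table to say so. SAP 9.5 states that no table shells will be provided, so programmers have only this text to follow.

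Gaps are possible under the schedule. After Day -1 of Period 2, chemistry is drawn on Days 11 and 18 and at follow-up. A subject who stops daily dosing on Day 5, for example, is exposed to the once-daily treatment but may have no Day 11 or Day 18 CPK. Safety and tolerability is a secondary objective, and with about eight subjects per treatment one missing result moves a percentage visibly.

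**Working it through.** The documents give no figure for this point, so there is none to reproduce. The check is direct arithmetic on the stated rule.

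**Inputs**

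- N, subjects exposed in a treatment: 8, the planned cohort size (Protocol 4.1, SAP 6.1).
- m, subjects with a result at the time point: 8, 7 or 6. The values 7 and 6 are assumptions for illustration, because the documents state no rate of missing laboratory or ECG results.
- a, subjects in a given abnormal category: 1, 2 or 3, also illustrative.

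**Formulas**

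- Percentage under the SAP rule = 100 × a/N.
- Percentage among subjects with a result = 100 × a/m.
- Ratio of the first to the second = m/N, whatever the category.
- Sum of all category rows under the SAP rule = 100 × m/N.

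**Results for N = 8**

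| m (missing) | a | SAP rule | Among measured | Difference, points | m/N | Rows sum to |
|---|---|---|---|---|---|---|
| 8 (0) | 1 | 12.5% | 12.5% | 0.0 | 1.000 | 100% |
| 7 (1) | 1 | 12.5% | 14.3% | 1.8 | 0.875 | 87.5% |
| 7 (1) | 2 | 25.0% | 28.6% | 3.6 | 0.875 | 87.5% |
| 7 (1) | 3 | 37.5% | 42.9% | 5.4 | 0.875 | 87.5% |
| 6 (2) | 1 | 12.5% | 16.7% | 4.2 | 0.750 | 75% |
| 6 (2) | 2 | 25.0% | 33.3% | 8.3 | 0.750 | 75% |
| 6 (2) | 3 | 37.5% | 50.0% | 12.5 | 0.750 | 75% |

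SAP 9.1.1 rounds percentages to integers, so one abnormal subject would print as 13% rather than 14% (one missing) or 17% (two missing).

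**The normal category moves by the same factor.** With one missing and one abnormal, six subjects are normal: 6/8 = 75.0% under the rule, 6/7 = 85.7% among those measured. With two missing and one abnormal, five are normal: 5/8 = 62.5% against 5/6 = 83.3%.

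**Replacements.** Protocol 4.1 allows for them: "Enrolled subjects who withdraw from the study may be replaced at the discretion of the Investigator and Sponsor". A replacement raises N and also supplies a result. If two subjects without results are replaced by two with results, N = 10 and m = 8. One abnormal subject is then 1/10 = 10.0% against 1/8 = 12.5%, a ratio of 0.80. Without replacement the ratio was 6/8 = 0.75. The relative shortfall falls from 25% to 20%.

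**The case against.** The strongest reply is that the rule is pre-specified and transparent, and that little turns on it. Much of that stands. The frequency tables show counts, and with about eight per treatment readers look at counts first. CPK and QTcF also have continuous summaries by scheduled time that show how many were measured and how many were missing. All laboratory and ECG values are listed by subject, and out-of-range laboratory values have their own listing. No hypothesis is tested. A reader who wants the other percentage can work it out.

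The chance of a missing result is also limited by design. Subjects are in-house throughout Period 2 dosing and until Day 19. Those who discontinue are to return 14 to 21 days after the last dose for a visit that includes laboratory tests and an ECG. Because the denominator is set per treatment, a subject who leaves before Period 2 is not counted in the Period 2 denominator.

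Two limits concern the text itself. The sentence in 17.1.3 covers urinalysis only, so the reach to CPK, QTcF and ECG conclusion rests on 9.1.3. And the frequency tables are not expressly laid out by visit: 9.1.4 says by time point where applicable. In a table with one entry per subject per treatment, exposed N would rarely exceed the number with at least one result.

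What survives is that no passage overrides the exposed denominator for these tables, and nothing in them would tell the reader how many subjects were measured.

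**Conclusion.** The point holds as a minor one. For tables of measured results the stated rule multiplies every category percentage by measured/exposed: 0.875 with one of eight missing and 0.75 with two of eight. For one to three abnormal subjects the gap is 1.8 to 5.4 percentage points in the first case and 4.2 to 12.5 in the second. It is zero when results are complete. These sizes rest on an assumed number of missing results and on tables laid out by time point.

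Four stronger readings are tempting, and the documents do not support them:

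- *A missing subject is counted as normal.* Missing laboratory and ECG results are not imputed, so the subject is in no category. The normal percentage falls too, and the shortfall from 100% is itself a sign of the gap.
- *The plan expects two of eight to lack safety results.* The target of at least six from eight concerns the primary PK analysis: the Day 1 dose and PK assessments to Day 10. It says nothing about laboratory or ECG completeness.
- *Replacements make the distortion worse.* They supply results of their own, and the relative shortfall gets smaller.
- *The exposed denominator biases abnormal rates and a measured denominator would not.* If subjects are lost because of a safety finding, the percentage among those measured is not unbiased either. What the change brings is a percentage with a clear meaning and a visible count of missing results.

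**What to change.** In SAP 9.1.3 and 17.1.3, state that frequency tables of measured results (urinalysis categories, CPK bands, QTcF bands, ECG conclusion) use as denominator the number of subjects in that treatment with a non-missing result for the parameter at that time point. For the QTcF change categories, require a baseline value as well. Show that number and the number missing beside N, in line with what 9.1.3 already asks for continuous variables. Keep exposed N for adverse events and concomitant medications.

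The cost is a sentence or two in the SAP and a changed denominator in the programs for these tables. No planned analysis is lost, and with complete data the tables report the same percentages as now.
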